6.2.2 Enrollment, Baseline, and/or Randomization

Enrollment

Participants will be enrolled in the study once they sign the informed consent form. Enrollment will be tracked in the study enrollment log.

Baseline Assessments

For participants who have successfully been screened for eligibility and are enrolled into the study, baseline assessments are performed against which to measure the study outcome. A complete list of the baseline evaluations are presented in Table 6.1.

Randomization

Randomization will precede the intervention.

We will allow a maximum of one month for the time between baseline assessment of participants and randomization; should more than one month pass for logistical reasons, baseline assessments would be repeated prior to randomization. Once participants complete eligibility and are randomized to a group, they will start treatment within 4 weeks.

6.2.3 Blinding

Independent evaluators will remain blind to treatment assignment throughout the study. To preserve the blind they will be instructed with a reminder script for patients not to discuss their treatment prior to an assessment. The randomization codes will be created by the study statistician prior to entry of the first patient in the trial. Randomization will be stratified only by site. No unblinded analyses will be performed prior to study completion, unless specifically requested by the DSMB, in which case study PIs will only see blinded safety comparisons of the study intervention groups.

The trainers/therapists and the person handling the randomization code cannot be blinded, but they will not be involved in IE ratings, which will be used for outcomes in this trial. The PIs will supervise the treatments, and oversee all study participants including safety and adverse events. The PIs will not, however, know the subject's patient codes and the PIs will not be involved in the independent evaluator ratings. Thus these clinical and oversight study staff will not have access to data and have no influence on the outcome data. Outcome ratings will be completed by the blinded independent evaluators. The data management and analysis will be completed by the study statisticians and data manager who are not involved in clinical treatment or safety assessment at any time.

6.2.4 Follow-up Visits

At mid-treatment visit (week 6 after enrollment), post-treatment assessment (Week 12-13) and 6month follow-up (Week 36-27):

- Clinical improvement (CGI-I)
- Self-report instruments (STAI, BDI-II, BAI, PSS, SCL-90, WHOQOL-BREF, MCQ, FFMQ, PSWQ, ISI, PSQI, ASQ)
- Psychophysiological/biological measures of stress (RSA, cortisol)
- Measures of study integrity and safety (Adverse Events, Concomitant Medications/Therapy log. homework compliance, working alliance)

6.2.5 Completion/Final Evaluation

See 6.2.4.

6.3 Visit Windows

If a subject cannot complete a study given visit within the windows specified below, all efforts should be made to have the subject's visit occur as close to the window as possible.

Any visits that occur out of window should be noted by the RA in the REDCap Protocol Deviation (PROTDEV) Log project.

Screening / Baseline

• <4 weeks should elapse between a subject's screening and baseline assessment.

• If a subject's baseline visit cannot be scheduled within 4 weeks of their initial screening visit (e.g., because their cohort does not fill up due to slow accrual), then they will need to be re-screened. At the re-screening visit, all Screening measures should be repeated, and the subject's SCID/ADIS GAD diagnosis should be confirmed.

Baseline / Treatment

• <4 weeks should elapse between a subject's baseline assessment and treatment initiation.

IE Assessments

- A window of +/- 7 days will be used for biweekly IE assessments
- A window of -30/+60 days will be used for the 6-month follow-up visit
- Week 6 and week 12 IE assessment should only occur after the week 6 and week 12 (i.e. final) treatment sessions (CBT, yoga, or SE), respectively.

Treatment Sessions

• No visit windows will be used for weekly group treatment sessions.

7. SAFETY ASSESSMENTS

For reasons of patient safety, patients who do not respond to SE after the 12 week intervention will be given the choice to receive CBT or yoga. Specifically, non responders (CGI-I>2) will be assisted in finding appropriate care from our existing referral resources. Additional treatments will be monitored and considered in the analyses. Subjects who wish to discontinue their participation at any point will also receive referral assistance if they request additional treatment.

Patients will be excluded if they report significant current suicidal ideation (as assessed with the BDI-II item 9 and CSS suicidality checklist) or suicidal behaviors within the past year. We will also exclude patients with seizures disorder resulting in ongoing cognitive impairment, patients with a history of head trauma causing loss of consciousness, seizures or ongoing cognitive impairment, patients with medical illnesses or instability for which hospitalization may be likely within the next year, and patients with physical conditions that might cause injury from yoga (e.g., physical injuries, musculoskeletal problems).

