The interventions include 12-week yoga, CBT, or stress education sessions. Independent clinical assessments will occur before the 12-session intervention phase, at mid-treatment, after the intervention, and at 6-month follow-up. We will allow a maximum of one month for the time between baseline assessment of participants and randomization; should more than one month pass for logistical reasons, baseline psychological assessments would be repeated prior to randomization. Once participants complete eligibility and are randomized to a group, they will start treatment within 4 weeks.

All 3 treatments will be administered in a group format to better reflect the most commonly available yoga format, and to maximize feasibility and cost-effectiveness (see also Integrity of Treatment Procedures). Providing all 3 modalities in the same sized and length group format will

also maximize integrity for the comparison of the active treatment components. All three treatments will be 2 hours in duration, allowing for 15 minutes of study logistics including discussion of subject questions or difficulties with the home or group interventions, evaluation of individual subject compliance, and strategizing enhancing compliance. The treatment itself will comprise a full 105 minutes training and practice in each group session. Subjects in all 3 treatment groups will be provided with a credible rationale for the efficacy of their assigned treatment. Subjects in the CBT arm will be informed of the role of CBT in the efficacy of changing dysfunctional thought patterns and beliefs, subjects in the yoga arm will be informed of the role of yoga in changing cognitive and physical emotional and stress reactivity through the postures, breath regulation and meditation components of yoga practice, and subjects in the Stress Education class will be informed about a variety of topics on stress and well-being: stress theory and physiology, effects of stress on body systems including cardiovascular and immunological, sleep efficiency, time management, nutrition, and exercise.

Sample Size and Population

We will randomize 230 patients with a primary diagnosis of GAD. Yoga (N = 95) will be compared to SE (N = 40), a commonly used control condition, and standard CBT for GAD (N = 95). All interventions will be conducted in a group format over 12 weeks with 4-6 patients per group and therapists/yoga instructors.

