diagnostic assessment. We conservatively estimate that 20% of eligible participants will discontinue the intervention prematurely, but all participants who are randomized will be included in the analysis with an intent to treat analytic approach. For ethical reasons, additional treatment will not be withheld for non responders (defined as CGI-I > 2) or anyone for whom additional intervention is indicated in any intervention condition during the 6 month follow up. Non responders (CGI-I>2) at week 12 will be assisted in finding appropriate care from our existing referral resources. All participants will receive 6 month assessments, but any additional treatment received by non responders will be adjusted for in the analyses.

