Non responders (CGI-I >2) will be assisted in finding appropriate care from our existing referral resources. Additional treatments will be monitored and considered in the analyses. Furthermore, subjects who wish to discontinue their participation at any point will also receive referral assistance if they request additional treatment.

If at any time during the course of the study, the DSMB judges that risk to subjects outweighs the potential benefits, the DSMB shall have the discretion and responsibility to recommend that the study be terminated.

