9.2 Sample Size and Randomization

A non-inferiority test is the most direct test of our hypothesis that Yoga will be as effective as CBT for both short-term and long-term outcomes. We will perform a non-inferiority test using response rate (response rate is defined as CGI-I ≤ 2) as the outcome on which to compare CBT and Yoga at posttreatment and at follow-up. Since some attrition may occur, we will use last observation carried forward to insure an intent-to-treat analysis. The non-inferiority margin will be half the difference in response rates between the active comparison (CBT) and placebo. Based on earlier literature, we can expect response rates in our particular CBT and placebo conditions of 57.9% in CBT and 22.2% in placebo. Thus, our non-inferiority margin will be set at ¹/₂ the difference between 56.7 and 22.2, or 17.85%. Using the power analysis program PASS 12, we find that the number of subjects required to obtain .80 power for the non-inferiority test comparing CBT and Yoga is 95 participants in each of the 2 conditions. We verified this number in a 1000 simulation Monte Carlo study using these same parameters. This number is higher than the number proposed in the original grant. Thus, we will increase the N per cell in CBT and Yoga to 95 (22 additional patients per site) to have adequate power for this non-inferiority test. While the original study was budgeted based on a lower number of participants, with careful management of costs we believe we can manage this increase in participants within the full study budget if awarded as proposed.

For the superiority tests (CBT vs. SE and Yoga vs. SE) on the secondary outcomes (which are continuous), we used the MRM power analysis program PinT 2.12. We assumed 25% missing data, and used data from our recent CBT trials (e.g., Stern et al., 2012) to estimate the variances and covariances needed for PinT. PinT indicated greater than .80 power to detect an effect size as small as d=.27, between a small (d=.20) and medium (d=.50) effect size.

We predict that changes in mindfulness will mediate changes in outcome over time for patients in the Yoga condition, and changes in cognitions will mediate changes in CBT. Plus, changes in RSA and cortisol may also mediate changes in outcome across conditions. We further predict that treatment condition will moderate the effect of Time on the mediators ("a" paths).

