To determine if the results of the analyses for Aim 1 are sensitive to the growth curve model, we will perform a secondary analysis, using a simple ANCOVA-type model, to verify the results of our primary growth curve model. Since the outcome is binary (response to treatment), this analysis will be performed using logistic regression, with the following predictors of outcome at post-treatment: baseline severity based on the CGI-S and SIGH-A, and the two dummy variables coding the contrast between SE and the 2 active treatments. This analysis will be performed twice: once as an ITT analysis with missing outcomes imputed as last observation carried forward, and once as a completer analysis.

Per Protocol Secondary Analysis:

As additional secondary analyses, we will repeat our GLMM and MRM analyses using the per protocol sample. We will use these analyses rather than simpler analyses (such as logistic regression or repeated measures ANOVA) because repeating our GLMM and MRMs will allow a more direct comparison to the results for the intent-to-treat sample, allows inclusion of subjects that miss some assessments (other than baseline and post-treatment), allows the modeling of complex covariances between the repeated measures, and it assumes MAR rather than MCAR.

Follow Up Secondary Analyses:

Analyses of outcome at FU (Aim 2) will be considered exploratory since subjects may seek additional treatment during follow-up. These analyses will follow the analyses of outcome at post-treatment, except one additional assessment (FU) will be added to these analyses. Since response during FU may not follow the growth curve of the treatment phase, the growth curve for Aim 2 will be modeled as "piecewise", separately modeling the growth curve during treatment and follow-up. (Analyses of the secondary outcomes at FU will follow the mixed effects ANOVA model described above since these analyses include only 4 total assessments). We will add an additional dummy variable predictor to the analyses for Aim 2, coding whether or not the subject received additional treatment during FU. We will also add the interactions of this "additional treatment" variable with all the other predictors in the analyses to determine if "additional treatment" impacted response to treatment at FU. This analysis will

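### The plan gives two rules for SE non-responders after week 12 (a choice of CBT or yoga, or referral only), so the control condition for the exploratory 6-month comparison with SE is undefined

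*Combined protocol and SAP*

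**What the plan says.** Section 7 (Safety Assessments) opens with a rule for one arm: "patients who do not respond to SE after the 12 week intervention will be given the choice to receive CBT or yoga". The sentence that follows is introduced as a specification of that rule, yet says only that non-responders "will be assisted in finding appropriate care from our existing referral resources".

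Section 3 (Study Design) gives the referral rule without naming an arm: "Non responders (CGI-I>2) at week 12 will be assisted in finding appropriate care from our existing referral resources". It also says that during the 6-month follow-up "additional treatment will not be withheld for non responders", and applies this to every condition. Section 8.1 repeats the referral rule: "Non responders (CGI-I >2) will be assisted in finding appropriate care from our existing referral resources".

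Aim 2 (Sections 1.1 and 9.1) predicts that yoga and CBT will each have a higher responder rate than SE at 6 months (Hypotheses 2.1-2.3). Section 9.1 labels Aim 2 exploratory, and Section 9.6 gives the possibility of additional treatment as the reason. For that analysis Section 9.6 adds a dummy variable "coding whether or not the subject received additional treatment during FU" and its interactions with all other predictors. It plans separate treatment contrasts for those with and without additional treatment, and a comparison of treatment-seeking across the three arms.

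**The concern.** A choice between the two treatments under test, offered to SE alone, is a different rule from referral help for non-responders in any arm. The 6-month control group differs accordingly. Under the first rule it is SE followed, for most participants, by an offer of yoga or CBT. Under the second it is SE followed by whatever outside care people find, with the same access in all arms. The plan leaves open which applies, who would deliver the CBT or yoga, and whether delivery precedes the 6-month visit. The two enrolling sites could each follow a different sentence in good faith and produce different control groups.

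At stake is the interpretation of the 6-month contrasts with SE. If many SE participants have had yoga or CBT by then, a small or null difference would say little about whether yoga or CBT outperforms SE.

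**Working it through.** **Inputs.** SE n = 40 and yoga and CBT n = 95 each (Précis, Section 3). Expected response is "57.9% in CBT and 22.2% in placebo" (Section 9.2); the placebo figure is used here for SE. Premature discontinuation is 20% (Section 3). Uptake of further treatment is not given, so it is varied.

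**Check of the rates.** The plan's non-inferiority margin is half the CBT-placebo difference: (57.9 - 22.2) / 2 = 35.7 / 2 = 17.85 points, which matches the stated margin. The 56.7 printed beside it would give 17.25, so 57.9 is the rate behind the plan's figure and is used below.

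**Number eligible for the choice.**
- All SE participants: 40 x (1 - 0.222) = 31.1, about 31 of 40.
- Only the 80% who do not discontinue: 32 x 0.778 = 24.9, about 25.
- Expected SE responders at week 12: 40 x 0.222 = 8.9, about 9.

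**Effect on the 6-month gap (illustration).** Assume that week-12 non-responders who take extra treatment respond at 57.9%, that all other statuses hold, and that yoga has the CBT rate. With uptake f among non-responders:
- SE rate = 0.222 + 0.778 x f x 0.579
- Active-arm rate if that arm also takes extra treatment = 0.579 + 0.421 x f x 0.579

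| Uptake f | SE rate | Gap if only SE takes extra treatment | Active-arm rate if all arms do | Gap if all arms do |
|---|---|---|---|---|
| 0 | 22.2% | 35.7 | 57.9% | 35.7 |
| 50% | 44.7% | 57.9 - 44.7 = 13.2 | 70.1% | 25.4 |
| 100% | 67.2% | 57.9 - 67.2 = -9.3 | 82.3% | 15.0 |

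Gaps are in percentage points, computed before rounding the rates.

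**Whether the planned adjustment repairs this.** Additional treatment arises after randomization and depends on week-12 non-response. If only non-responders take it, the SE stratum without additional treatment holds the 8.88 expected responders plus 31.12 x (1 - f) non-responders. Its week-12 response rate is then:
- f = 50%: 8.88 / (8.88 + 15.56) = 36.3%
- f = 75%: 8.88 / (8.88 + 7.78) = 53.3%
- f = 100%: 8.88 / 8.88 = 100%

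The rate as randomized is 22.2%. Selection alone therefore moves the untreated SE stratum, and at high uptake it is mainly the 9 or so responders. Interactions with the dummy estimate contrasts within such strata; they do not remove the selection. The dummy is also yes/no, so it cannot separate an SE participant who received CBT or yoga from one who received other care.

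**The case against.** The strongest reply is that the plan has foreseen this. Aim 2 is labelled exploratory because participants may seek more treatment. The primary week-12 analysis excludes follow-up data. Additional treatment is logged at the 6-month visit (Section 6.1), modelled with interactions, and compared by arm. All of this is correct, and it limits the consequence to an exploratory aim. It does not settle which rule the SE arm is under, and stratifying on a post-randomization variable does not recover the randomized comparison.

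A second reply concerns the reading of Section 7. Because the referral sentence is presented as a specification of the one before it, the choice of CBT or yoga may simply be carried out through referral. That reading is possible. A reader might infer instead that SE non-responders cross over to the trial's own groups. The documents do not support that as settled: they mention no study sessions, therapists or manuals for this purpose. Nor does a referral-only rule keep SE participants away from CBT.

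Third, a reader might infer from the SE-only column that the 6-month result would vanish or reverse. That column gives no extra treatment to yoga or CBT non-responders, although Section 3 allows it in every arm. Under the same assumptions in all arms, the gap stays at 25.4 points at 50% uptake and 15.0 points at 100%. The reversal needs full uptake in SE and none elsewhere.

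Finally, a reader might see a threat to evaluator blinding. Section 6.2.3 keeps evaluators blind throughout and already has a script asking patients not to discuss treatment. A control who mentions yoga would, if anything, point the evaluator to the wrong arm.

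**Conclusion.** The contradiction is real, both inside Section 7 and between Section 7 and Sections 3 and 8. As written, the plan does not define the control condition for the 6-month contrasts with SE in Hypotheses 2.1-2.3. Up to about 31 of 40 SE participants (about 25 counting only those who do not discontinue) would be eligible for the choice. This is an upper bound on exposure, resting on the 22.2% placebo rate holding in SE. Actual exposure could be anywhere from none to all of them.

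The possible dilution is material but its size is unknown. At 50% uptake the gap would be 13.2 to 25.4 points instead of 35.7, depending on whether the active arms also take extra treatment, and assuming a 57.9% response among those who take it. The planned adjustment would not resolve this at high uptake. It would be wrong to infer that the primary result is compromised, since the choice comes only after week 12. The point should be addressed, in proportion to an exploratory aim.

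**What to change.** 1. Reconcile Sections 3, 7 and 8.1 into one post-week-12 rule and say whether it is the same in all arms. State whether any CBT or yoga offered is study treatment and how its timing relates to the 6-month visit. The choice of rule is the sponsor's.
2. On the existing Concomitant Medications/Therapy Log, record the type (CBT, yoga, other) and start date of any treatment begun after week 12. Use that type, in place of a bare yes/no code, in the Aim 2 analysis.
3. If the SE-only choice stays, state that the 6-month SE contrast compares strategies, with the control being SE followed by a choice of CBT or yoga, and that it does not test Hypotheses 2.1-2.3 against SE as worded.

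The cost is a wording change, one added log field and, if the SE-only choice stays, a narrower Aim 2 claim against SE. No change to the visit schedule or to the evaluator script is needed.

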7.1 Specification of Safety Parameters

A study MD or nurse with MD oversight will assess medical history and with consent will consult with PCPs if any medical issues that may potentially interfere with safe participation in yoga are identified. We have modified our study criteria to more clearly exclude all potential subjects with physical disabilities (evaluated with a medical history and physical exam) or cognitive disabilities (evaluated by the Montreal Cognitive Assessment Scale) that would clearly preclude safe practice of the yoga intervention or CBT. At present there is insufficient information regarding the safety of yoga during pregnancy. For reasons of safety, all women of childbearing potential will be required to use a reliable form of birth control throughout the study: (e.g.: oral contraceptives, surgical sterilization (of the subject or of her male partner), IUD (intrauterine device), condom and spermicide or diaphragm and spermicide). Subjects with existing or planned pregnancy during the intervention will be excluded. Inclusion of subjects

with any minor preexisting conditions of potential concern will be subject to participation only after consented review with and approval by the subject's primary healthcare provider.

Each visit, adverse events will be assessed on the adverse events monitoring form and rated as mild, moderate, or severe (as defined in AE section below). On weeks 0, 2, 4, 8, 10 and 12 the CGI-S, CGI-I, BDI and a suicidality checklist will be administered to evaluate any potential worsening symptoms. Physical fitness will be assessed by the study nurse with MD oversight or MD with the medical history form and a standard physical exam, emphasizing musculoskeletal, neurologic and cardiac history.

Twenty-four-hour emergency coverage with a study clinician (physician, psychologist or registered nurse with MD oversight) will be available. Patients will be provided with cards with the emergency contact number. In the event of an emergency the clinician will determine the necessary clinical intervention and will provide and coordinate appropriate care.

Parameters

All three interventions (Yoga, CBT, and SE) are safe interventions with minimal associated risk.

We anticipate minimal risk to subjects due to their participation in this study; however, some risks are associated with conducting these treatments. The primary risk is the evocation of uncomfortable levels of anxiety or other emotions during some treatment sessions. Some patients may find sessions stressful and react to them with anxiety. However, it is not expected that anxiety will be higher than what they would experience in other life situations. Participants will be informed about these risks and told that they may withdraw from the study at any time and may refuse to complete any treatment procedures they find too uncomfortable. Some patients may feel uncomfortable about the treatment sessions being taped (necessary for supervision and treatment adherence checks). However, this will be a required procedure. The purpose of the taping will be explained, confidentiality will be maintained, and informed consent for taping will be obtained. Additionally, clients may experience some disruption of daily activities due to scheduling of treatment sessions.

There is a possibility that a patient may become distressed when being asked about symptoms or personal experiences during the diagnostic evaluation or assessment sessions. The primary risks to the patient are discomfort associated with the assessments and the treatment procedures. Subjects may also experience some discomfort or anxiety from discussing personal information. Yet, this anxiety is not expected to be any greater than that subjects already experience, and subjects will be able to withdraw from the study at any time. There are risks of injury during yoga. The practice of the physical exercises and postures, breathing exercises, relaxation techniques, and meditation in the yoga treatment involve little risk, although at times subjects may find them challenging and difficult to complete. Overexertion on the physical exercises may lead to temporary muscle soreness for up to a week. However, subjects will be instructed to gradually increase their effort on the physical exercises and breathing practices so as not to overexert themselves, and to stop if any subjects experience unexpected unpleasant symptoms. There may be risks and side effects that are currently unknown and/or unanticipated.

Study personnel will be monitoring the patients' clinical and physical conditions carefully and will withdraw patients from the study if warranted by their clinical condition. The yoga instructor will again review all preexisting conditions with subjects in the group at the beginning

of the 12-week intervention and will make modifications to the practices as necessary to ensure subject safety and to prevent injury. The instructor will also require subjects to report any recent changes in their health, injuries or conditions at the beginning of every treatment session. Group size will be relatively small for yoga classes with 4-6 subjects per group, which allows for careful monitoring of subject safety during the class sessions.

In addition to the risks associated with the treatments, interviews, and questionnaires, there are some other potential risks from the electrocardiograms, such as an allergic reaction to the electrode paste. However, these reactions are rare and typically very mild.

Although every effort will be made to assure confidentiality, it is possible someone could without permission gain access to study related data during the time they are being used or stored for examination of results.

